**Local Supplement to Sponsor Protocol (HRP-508)****INSTRUCTIONS:**

- *Only use this form when also providing a protocol (not just a grant application) from a sponsor or lead site (e.g. commercial, NIH, etc.). For all other protocols use HRP-503.*
- *Depending on the nature of your study, some sections may not be applicable to your research. If so, you must provide the reason why the section is not applicable. For example, when accurate, the statement, "local inclusion criteria will not differ from those of the sponsor's protocol" could be provided in response to question 1.1.*
- *Provide the entire Sponsor protocol as a separate upload in Click IRB.*
- *Unless otherwise specified, provide only site-specific information below.*
- *When you write a single site supplement, keep an electronic copy. You will need to modify this copy when making changes. When you make changes, use the Track Changes feature.*
- *Do not remove the italics instructions or headings.*
- *If you are pasting information from other documents be sure to use the "Merge Formatting" paste option so that the formatting of the response boxes is not lost. If information is presented outside of the response boxes, it may not be accepted.*
- *If this study involves multiple participant groups who participate in different research procedures, consent processes, etc., be certain to provide information in each applicable section for each participant group and clearly label each participant group within a section or subsection.*

### **FUNDING:**

*Indicate any funding for this proposal. This should match the Funding Sources page in Click IRB.*

Response: Buffalo Neuroimaging Analysis Center

### **GRANT APPLICABILITY:**

*Describe whether or not this protocol is funded by a grant or contract and if so, what portions of the grant this study covers.*

Response: Not applicable.

### **VERSION NUMBER/DATE:**

*Include the version number and date of this site supplement.*

Response: 5, 03MAR23

### **Revision History**

Revision #	Version Date	Summary of Changes	Consent Change?
1	24/06/2021	Change based on the new study protocol	Yes
2	28/02/22	Addition of Dent Institute as a recruitment and testing site	New MS consent for DENT; Yes to current MS consent form

PROTOCOL TITLE: Open-label, single-blinded, observational, prospective, 36-month, longitudinal, controlled study to assess the efficacy of siponimod (Mayzent®) on microglia in patients with secondary progressive forms of multiple sclerosis

3	07/04/2022	Inclusion of 15 healthy controls to undergo 1 PET scan and 1 MRI scan.	New HC consent form
4	11/9/2022	Including Great Lakes Medical Imaging as a PET scanning site	No
5	03/03/2023	Closing enrollment and follow-up of MS patients; Closure letter; continued enrollment of HCs	Yes - HC

PROTOCOL TITLE: Open-label, single-blinded, observational, prospective, 36-month, longitudinal, controlled study to assess the efficacy of siponimod (Mayzent®) on microglia in patients with secondary progressive forms of multiple sclerosis

## 1.0 Study Summary

Study Title	Open-label, single-blinded, observational, prospective, 36-month, longitudinal, controlled study to assess the efficacy of siponimod (Mayzent®) on microglia in patients with active secondary progressive forms of multiple sclerosis
Study Design	Open label, single-blinded, observation, prospective, longitudinal BNAC MRI analysts are blinded to subject's medication treatment.
Primary Objective	The assessment of the effect of Mayzent over at least 24 months on the evolution of microglia pathology in patients with active secondary-progressive (SP) MS.
Secondary Objective(s)	(a) compare the effect of Mayzent to the control group of active SPMS patients treated with ocrelizumab (Ocrevus®), as measured by changes in microglial activation in the lesional and non-lesional normal appearing (NA) WM and GM, and in the peri-plaque area of chronic lesions in the brain; (b) the relationship between changes in microglial activation in the lesional and non-lesional normal appearing

PROTOCOL TITLE: Open-label, single-blinded, observational, prospective, 36-month, longitudinal, controlled study to assess the efficacy of siponimod (Mayzent®) on microglia in patients with secondary progressive forms of multiple sclerosis

	
(NA) WM and GM, and in the peri-plaque area of chronic lesions in the brain and clinical and behavioral outcomes.
 
(b) to validate the quantification approach and to use as a statistical control group (15 HCs) when looking at an increase in TSPO in a parametric map of the brain

Research Intervention(s)/ Investigational Agent(s)	MRI and PET scans, clinical visits, questionnaires, eye exam, blood sampling.
IND/IDE #	
Study Population	
Individuals with active Secondary Progressive Multiple Sclerosis (SPMS)
 
Activity is determined by MRI activity (contrast-enhancing lesions; new and unequivocally enlarging T2 lesions) and/or clinical relapses in the 24 months prior to the study baseline.
 
15-age-matched healthy controls (10 females and 5 males aged between 18-65 years)

Sample Size	60 MS patients; 15 healthy controls
Study Duration for individual participants	
2-3 years: MS Patients
 
Approximately 4 hours: healthy controls – 1 timepoint

Study Specific Abbreviations/ Definitions	

AEs	Adverse Events
BBB	Blood-brain-barrier
BICAMS	Brief International Cognitive Assessment for MS
BNAC	Buffalo Neuroimaging Analysis Center
BVMT-R	Brief Visuospatial Memory Test – Revised
CE	Contrast Enhancing
CNS	Central Nervous System
CRFs	Clinical Research Forms
CSF	Cerebrospinal fluid
CVLT-II	California Verbal Memory Test – Second Edition
3-D	Three Dimensional
EDSS	Expanded Disability Status Scale
ECG	Electrocardiogram
ELISA	Enzyme-linked immunosorbent assay
ETL	Echo Train Length
FLAIR	Fluid-Attenuated Inversion Recovery
FLIRT	FMRIB's Linear Image Registration Tool

PROTOCOL TITLE: Open-label, single-blinded, observational, prospective, 36-month, longitudinal, controlled study to assess the efficacy of siponimod (Mayzent®) on microglia in patients with secondary progressive forms of multiple sclerosis

FMRIBs	Functional MRI of the Brain
FOV	Field of View
FSE	Fast Spin Echo
FSPGR	Fast Spoiled Gradient Echo
GFAP	Glial fibrillary acidic protein
GE	General Electric
GM	Gray Matter
GRE	Gradient Echo Sequence
HAB	High affinity for DNA polymorphism of the TSPO gene on chromosome 22q13.2 SNP
HD	High Definition
HDNV	Head and Neck Neurovascular Coil
HIPAA	Health Insurance Portability and Accountability Act
HIRES	High Resolution
IEC	Independent Ethics Committee
IR	Inversion Recovery
IRB	Investigational Review Board
IR-FSPGR	Inversion Recovery-Prepared fast Spoiled Gradient Recalled Sequence
ITT	Intention-to-Treat
LAB	Low affinity for DNA polymorphism of the TSPO gene on chromosome 22q13.2 SNP
LCLA	Low contrast letter acuity
LV	Lesion volume
MAB	Co-expression of LAB and HAB affinity for DNA polymorphism of the TSPO gene on chromosome 22q13.2 SNP
MR	Magnetic Resonance
MRI	Magnetic Resonance Imaging
MS	Multiple Sclerosis
MTR	Magnetization transfer ratio
NA	Normal appearing
9-HPT	Nine-Hole Peg test
OCT	Optical coherence tomography
PBR	Peripheral benzodiazepine receptor
PBVC	Percent brain volume change
PCVC	Percent cortical volume change
PD	Proton Density
PET	Position emission tomography
PI	Prescribing information
PTVC	Percent thalamic volume change
RCP	Radiochemical purity
ROI	Region of interest
QSM	Quantitative susceptibility mapping
REB	Research Ethics Board

PROTOCOL TITLE: Open-label, single-blinded, observational, prospective, 36-month, longitudinal, controlled study to assess the efficacy of siponimod (Mayzent®) on microglia in patients with secondary progressive forms of multiple sclerosis

SAEs	Serious Adverse Events
SD	Standard Deviation
SDMT	Symbol Digit Modalities Test
SE	Spin Echo
SIENA	Structural Image Evaluation, using Normalization of Atrophy
SIENAX	Structural Image Evaluation, using Normalization of Atrophy Cross-Sectional
sNfL	Serum neurofilament light chain
SNP	Single nucleotide polymorphism
SPGR	Spoiled Gradient Recalled Acquisition
SPMS	Secondary-progressive multiple sclerosis
SPSS	Statistical Package for the Social Sciences
TE	Echo Time
TI	Inversion Time
T25FW	Timed 25-Foot Walk
TR	Repetition Time
TSPO	18 kDa translocator protein
USPIO	Ultrasmall superparamagnetic iron oxide particles
VOI	Volume of interest
VT	Volume of distribution
VZV	Varicella zoster virus
WB	Whole Brain
WI	Weighted Image
WM	White Matter

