## 11.0 Local Number of Subjects

*11.1 Indicate the total number of subjects to be accrued locally.*

Response: 60 MS (no longer applicable); 15 HCs

*11.2 If applicable, distinguish between the number of subjects who are expected to be enrolled and screened, and the number of subjects*

PROTOCOL TITLE: Open-label, single-blinded, observational, prospective, 36-month, longitudinal, controlled study to assess the efficacy of siponimod (Mayzent®) on microglia in patients with secondary progressive forms of multiple sclerosis  
*needed to complete the research procedures (i.e., numbers of subjects excluding screen failures.)*

- Response: We estimate that 90 MS patients will need to be screened in order to achieve our enrollment goal of 60. *No longer applicable*
- Healthy control subjects will be from other studies which they participated in and consented to be contacted for participation in future studies.

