## **16.0 Consent Process**

*16.1 Indicate whether you will be obtaining consent.*

Response: Yes.

*16.2 Describe where the consent process take place.*

Response: Consenting will take place in a private room within BNAC UBMD Neurology, or Dent (no longer applicable).

*16.3 Describe any waiting period available between informing the prospective subject and obtaining the consent.*

Response: When subjects are approached about participation in this study they can either choose to be consented and start the screening process at

PROTOCOL TITLE: Open-label, single-blinded, observational, prospective, 36-month, longitudinal, controlled study to assess the efficacy of siponimod (Mayzent®) on microglia in patients with secondary progressive forms of multiple sclerosis that time, or they can contact a study coordinator at a later date of their choosing.

*16.4 Describe any process to ensure ongoing consent.*

Response: If there are any changes to the study procedures (*see study closure letter for patients*), subjects will be informed (possibly even asked to sign a new consent based on the change). The subjects are reminded that participation is voluntary and they are free to stop participating at any time without penalty or change to their clinical care.

*16.5 Describe whether you will be following “SOP: Informed Consent Process for Research (HRP-090).” Pay particular attention to Sections 5.4-5.9. If not, or if there are any exceptions or additional details to what is covered in the SOP, describe:*

- *The role of the individuals listed in the application as being involved in the consent process.*
- *The time that will be devoted to the consent discussion.*
- *Steps that will be taken to minimize the possibility of coercion or undue influence.*
- *Steps that will be taken to ensure the subjects’ understanding.*

Response:  We have reviewed and will be following “SOP: Informed Consent Process for Research (HRP-090).”

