## Statistical Analysis Plan

**“Open-label, single-blinded, comparative, prospective, 36-month, longitudinal, controlled study to assess the efficacy of siponimod (Mayzent®) on microglia in patients with active secondary progressive forms of multiple sclerosis”**

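### The Study Summary and SAP still state 60 MS patients and a 24- to 36-month horizon after version 5 closed MS enrolment and follow-up

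*Combined protocol and SAP*

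**What the plan says.** **Study Summary (section 1.0), current in version 5.** The primary objective is "The assessment of the effect of Mayzent over at least 24 months on the evolution of microglia pathology". The sample size is "60 MS patients; 15 healthy controls" and the individual duration is "2-3 years: MS Patients". None of these entries carries a qualifier.

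**Elsewhere in version 5.**
- The Revision History entry for version 5, dated 3 March 2023, reads "Closing enrollment and follow-up of MS patients; Closure letter; continued enrollment of HCs".
- Section 11.1 gives the local number as "60 MS (no longer applicable); 15 HCs". Section 11.2 retires the screening estimate of 90 in the same way, and sections 8.2 and 10.3 do so for MS recruitment.
- Section 16.4 refers the reader to a letter: "see study closure letter for patients".
- Section 10.5 still describes payment for five MS visits.
- The Revision History entry of 28 February 2022 is "Addition of Dent Institute as a recruitment and testing site".

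**SAP, dated 15 September 2023.** The title still describes a "comparative, prospective, 36-month, longitudinal, controlled study to assess the efficacy of siponimod". Under MRI Analysis, Lesion activity, the cumulative number of contrast-enhancing gadolinium and USPIO lesions is built from four windows: 0–6, 6–12, 12–24 and 24–36 months. The opening text calls the sample small and the study exploratory. It gives no number of patients or scans at any visit, does not mention the closure, and has no rule for windows that were not completed.

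**The concern.** The Study Summary is where a reader learns what the primary objective can claim: how long patients were observed and how many there were. Version 5 says elsewhere that MS enrolment and follow-up have closed, yet the summary's horizon and sample size stand as if nothing had changed. The SAP was written after the closure and in the past tense, and it repeats the long horizon. A reader of the Study Summary and the SAP title would expect 24- to 36-month data on up to 60 patients. Neither place says whether such data exist.

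A smaller consequence concerns the lesion counts. If patients entered at different times and follow-up stopped on one date, they have different numbers of contrast scans. A cumulative count compared across such patients would mix lesion activity with the number of scans. The SAP does not say how it deals with this.

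**Working it through.** **The planned figure.** The 60 cannot be reproduced. These documents give no effect size, standard deviation, power or dropout rate behind it. The check is therefore of dates and of one passage against another.

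**Inputs.** Version 5: 3 March 2023 (Version Number/Date; Revision History). Dent added: 28 February 2022 (Revision History). Earliest dated revision: 24 June 2021 (Revision History). SAP: 15 September 2023. Months are days divided by 30.4375.

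**Step 1: closure to SAP.** 3 March 2023 to 15 September 2023 = 196 days = 6.4 months. The SAP follows the closure.

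**Step 2: entry dates that the stated horizon needs, if follow-up ended on the version date (assumption).**
- 24 months: entry by 3 March 2021.
- 36 months: entry by 3 March 2020.

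**Step 3: longest possible follow-up by entry date.** First entry is not given, so the entry dates below are assumptions taken from the dated revisions.

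| Entry no earlier than | To 3 March 2023 | To 15 September 2023 |
|---|---|---|
| 28 February 2022 (Dent added) | 368 days = 12.1 months | 368 + 196 = 564 days = 18.5 months |
| 24 June 2021 (revision 1) | 617 days = 20.3 months | 617 + 196 = 813 days = 26.7 months |

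The first row covers every patient recruited through Dent after its addition, and anyone else entering from that date. Such a patient falls short of 24 months on either end date. The second row applies only if no MS patient entered before revision 1, which the documents do not say. Entry before March 2021 would allow 24 months for some patients.

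**Step 4: visits.** The SAP windows imply visits at 0, 6, 12, 24 and 36 months, which matches the five visits in section 10.5. With 12.1 months, a patient can have at most 3 of the 5 (0, 6 and 12 months).

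**Step 5: cumulative lesion count, illustration only.** Assume a constant number of lesions per scan. The share of a 36-month count is then scans done divided by scans possible.

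| Last visit | Follow-up scans only | Baseline scan also summed |
|---|---|---|
| 6 months | 1/4 = 25% | 2/5 = 40% |
| 12 months | 2/4 = 50% | 3/5 = 60% |
| 24 months | 3/4 = 75% | 4/5 = 80% |
| 36 months | 4/4 = 100% | 5/5 = 100% |

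The SAP does not say whether the baseline scan is summed. On this assumption a patient last seen at 12 months contributes about half (50–60%) of a full count.

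**The case against.** **The retired target may only mean that accrual is over.** Section 11.1 answers a question about subjects to be accrued, and the other retired items also concern recruitment. That reading is open. A reader might infer that the trial missed its 60 patients. The documents do not support this, because the achieved number is nowhere stated. The Study Summary would still need reconciling, because the closure also covers follow-up.

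**The end of follow-up is explicit only in the Revision History.** This is true, with indirect support from the closure letter cited in section 16.4. But the version 5 entry describes what the current version does, not superseded text. The version date is also not a documented last-visit date, which is why the working carries the range to the SAP date.

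**A reader might infer that nobody reached 24 months, or that Dent recruits form a large short-follow-up group.** Neither is shown. First entry is unknown, and so is whether Dent enrolled anyone.

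**Lesion counts are outside the Study Summary's objectives.** This stands, so that part is secondary. The SAP's four windows can also be read as separate totals per interval, and it does not say that incomplete patients enter a single 36-month sum or that such a sum is compared between arms. It is tempting to call the siponimod–ocrelizumab comparison biased. Unequal scan numbers are noise unless follow-up differs by arm. That is possible without randomisation, but it is not shown.

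**The SAP acknowledges a small sample and an exploratory study.** It does, but this is neither an account of the closure nor a count per visit.

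**Other documents may hold the answer.** The sponsor protocol and the closure letter are separate and were not available. They could contain closure or missing-data rules, but the Study Summary and SAP would still need to agree with them.

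**Conclusion.** The inconsistency is real and should be fixed. Version 5 closes MS enrolment and follow-up and marks the 60 as no longer applying, while its own Study Summary keeps 60 patients, 2 to 3 years and a 24-month minimum without comment. The later SAP keeps the 36-month label and the last lesion window.

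What can be sized is a ceiling for one group: 12.1 months for anyone entering on or after 28 February 2022 if follow-up ended on the version date, and 18.5 months if it ran to the SAP date. For such patients the stated horizon cannot hold. The effect on the primary objective as a whole cannot be sized, because entry dates, last visits and achieved N are not given. Confidence in the contradiction is high; confidence in its effect on the results is moderate at most.

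The lesion-count issue is a request for clarification and a safer analysis. It is not a demonstrated bias.

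**What to change.** **1. Study Summary and SAP (main change).** Reconcile both with the Revision History and sections 11.1 and 16.4:
- Keep 60 patients and 24–36 months, labelled as planned.
- Beside them state the closure, its date, and the achieved N per arm at 0, 6, 12, 24 and 36 months.
- Limit the primary objective's horizon to what was observed, and draw no 24- or 36-month conclusion where those visits were not reached.

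**2. SAP, lesion activity (secondary).**
- Do not compare raw cumulative gadolinium and USPIO counts across patients with different numbers of scans.
- Compare them within a common window that both arms reached, for example baseline to 12 months, using the Mann-Whitney test the SAP already names.
- Give the count per follow-up scan as a sensitivity analysis only. If activity changes over time, it still depends on follow-up length, because patients followed briefly supply only early scans.
- State whether the baseline scan is summed, and drop windows left empty by the closure.

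**Cost.** Wording in two places, a table of numbers by arm and visit, and a small re-analysis of existing data. A common window leaves out later scans and any patient who did not reach its end. The stated horizon and N will look less favourable, and a 24- or 36-month conclusion may have to be given up.

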**2023-09-15**

All statistical analyses were performed using SPSS version 28.0 (IBM, Armonk, NY, USA). The data distribution was determined using visual inspection of the histograms and Q-Q plots.

Categorical data was compared using chi-square test, parametric numerical data was compared using Student's t-test and non-parametric data using Mann Whitney U test. The comparisons between the groups were further adjusted for demographic and genetic differences using analysis of covariance (ANCOVA) and adjusted estimated means were shown as mean (standard error).

Due to the small sample size and non-parametric nature of the data, the correlations were performed using non-parametric Spearman's test. Pair-wise comparisons within the subjects were also performed. P-values lower than 0.05 were considered statistically significant. Due to the exploratory nature of the study, corrections for multiple comparisons were omitted. The data was additionally visualized using box and scatter plots.

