#### **PET analysis:**

Prior to regional analysis, subject-specific SUV maps were created. First, list-mode data was reconstructed into 5-minute frames and then aligned in order to correct for patient motion (see Figure 6 for further details). Next, aligned, decay-corrected activity maps were combined and then converted to voxel-wise standardized uptake value (SUV) maps (Figure 7) based on injected dose (ID) and body weight (BW) at the time of injection, using the formula  $SUV = C_{img}/(ID/BW)$ . To facilitate subsequent regional analysis, SUV maps were fused with MRI using the CT scan as an anatomical proxy.

For lesional and non-lesional NAWM and NAGM, and the peri-plaque area of chronic lesions in the brain analyses, the derived regions and/or expert-traced regions of interest (ROIs) from the fused MRI were applied to the PET scans to determine lesional and non-lesional  $^{18}\text{F}$ -PBR06 binding. To correct for individual variation in tracer kinetics, SUV measures were referenced to the mean SUV of the cerebellum to produce relative SUVR measures for each relevant region of interest. Additionally, to correct for partial voluming of the larger PET voxels compared to MRI, region-based voxel-wise (RBV) correction combined with the reblurred Van-Cittert (RVC) was employed using PETPVC.

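### The SAP gives no test or threshold for the parametric-map objective; its general rule of uncorrected p < 0.05, if applied per voxel, would on average mark 25–70 cm³ of unaffected brain as increased

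*Combined protocol and SAP*

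**What the plan says.** In the local supplement, section 1.0 (Study Summary), the second item labelled (b) under the secondary objectives gives the healthy controls two purposes. One is to validate the quantification. The other is "to use as a statistical control group (15 HCs) when looking at an increase in TSPO in a parametric map of the brain". The Revision History records the matching change: "Inclusion of 15 healthy controls to undergo 1 PET scan and 1 MRI scan".

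The SAP's general statistical section, dated 2023-09-15, sets one criterion for everything: "P-values lower than 0.05 were considered statistically significant". It adds: "Due to the exploratory nature of the study, corrections for multiple comparisons were omitted". No exception is made for the map. The tests named are chi-square, Student's t, Mann–Whitney, ANCOVA, Spearman correlation and within-subject pairwise comparisons. On software it says: "All statistical analyses were performed using SPSS version 28.0". No tool for voxel-wise testing is named.

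The SAP's PET analysis section says that activity images are "converted to voxel-wise standardized uptake value (SUV) maps", but presents this as preparation: "Prior to regional analysis, subject-specific SUV maps were created". The outcome it goes on to define is regional: "SUV measures were referenced to the mean SUV of the cerebellum to produce relative SUVR measures for each relevant region of interest". Neither document states, for the parametric map, the unit of comparison, the direction of the test, a voxel or cluster threshold, or a minimum extent.

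**The concern.** Waiving multiplicity correction is defensible for a handful of exploratory regional comparisons, provided it is disclosed, as it is here. A parametric map is a different object. Its result is the set of locations called increased, and it involves a very large number of tests. A valid test at 0.05 in each voxel marks a predictable average share of unaffected brain as increased. Calling the study exploratory does not change that share.

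The objective is stated and the only decision rule in the plan is uncorrected. An analyst who follows the SAP as written therefore has nothing that limits false signal in the map. At stake is whether a reported pattern or extent of raised TSPO relative to controls can be told apart from chance. The Revision History also shows that enrolment and follow-up of MS patients have closed while control enrolment continues, and this map is one of the two stated reasons for having those controls.

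**Working it through.** The documents give no power, sample-size or false-positive figure for the map, so there is no stated figure to reproduce.

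**Inputs.**
- Controls: n = 15 (section 1.0 and Revision History).
- Significance level: 0.05, direction not stated (SAP), so both cases are shown: upper-tail rate 0.05 if one-sided, 0.025 if two-sided.
- Multiplicity correction: none (SAP).
- Analysed brain volume V: not in the documents; assumed 1,000–1,400 cm³.

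**Step 1. Average false volume if p < 0.05 is applied per voxel.** Expected volume = upper-tail rate × V. This holds for any valid per-voxel test, whether by patient or by group, and whatever the spatial correlation.
- Two-sided, upper tail: 0.025 × 1,000 = 25 cm³; 0.025 × 1,400 = 35 cm³.
- One-sided: 0.05 × 1,000 = 50 cm³; 0.05 × 1,400 = 70 cm³.

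**Step 2. Chance of at least one false signal.** Take independent resolution elements of volume FWHM³, with an assumed smoothness of 6–10 mm. Their number runs from 1,000 (V = 1,000 cm³, 10 mm) to about 6,500 (V = 1,400 cm³, 6 mm). Even in the mildest case, 1 − (1 − 0.025)^1000 is 1 to ten decimal places.

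**Step 3. How far a single patient can differ from the average.** A patient with no increase was simulated against 15 controls (400 runs, 1,206 cm³ mask, exact single-case t test). The noise correlation is assumed.

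| Noise | One-sided: mean (95% range), cm³ | Upper tail of two-sided: mean (95% range), cm³ | Share of patients under 10 cm³ (one-sided / upper tail) |
|---|---|---|---|
| FWHM 8 mm | 60 (50–71) | 30 (24–38) | – |
| FWHM 20 mm | 59 (25–108) | 29 (10–62) | – |
| FWHM 8 mm, 20% of variance shared brain-wide | 62 (4–214) | 31 (2–119) | 10% / 29% |
| FWHM 8 mm, 50% of variance shared brain-wide | 62 (0–457) | 33 (0–265) | 49% / 67% |

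The mean barely moves; the spread between patients becomes very wide.

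**Step 4. Effect of having only 15 controls, if single-patient maps are made.** If a patient were judged by a normal cut-off z on the control mean and SD, the true upper-tail rate would be P(t₁₄ > z/√(1 + 1/15)).
- z = 1.96: 3.9% instead of 2.5%, or 39–55 cm³ over the assumed volumes.
- z = 1.645: 6.7% instead of 5%, or 67–94 cm³.

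The plan states no such cut-off. This step only shows why the reference distribution needs to be written down.

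**Step 5. What stricter thresholds do.** A per-voxel p < 0.001 gives 0.001 × V = 1.0–1.4 cm³ on average. Bonferroni over 1,000 to about 6,500 elements (0.05/1,000 = 5 × 10⁻⁵, down to about 8 × 10⁻⁶) would require a single patient to lie about 5.5–6.7 control SDs above the control mean. False-discovery-rate and cluster methods would differ, but this illustrates the cost in sensitivity.

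**The case against.** The strongest reply is that the voxel classifier is not in the documents. The SAP treats voxel-wise SUV maps as a step towards regional analysis, its outcome is SUVR by region, and its tests are subject-level tests in SPSS. On that reading the waiver was written for regional comparisons, where it is acceptable, and the map is simply undescribed. The supplement's instructions also say that a full sponsor protocol is filed separately. That protocol was not among the documents reviewed and might define the map.

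Much of this stands. A reader might infer that the plan classifies each patient's voxels at 0.05, or that it uses a cut-off of control mean plus 1.96 SD. The documents state neither, and a control group serves a group comparison equally well. A reader might also infer that every patient without an increase will show tens of cubic centimetres. Step 3 shows that this is an average and not a certainty. Finally, a chance rate of 2.5–5% does not by itself make every map look widely abnormal, since extent above a known chance rate can still be interpreted.

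The reply does not remove the point. The objective names the map, the SAP carves out no exception, and its one decision rule is uncorrected. Either that rule governs the map, with the average false volume in step 1, or a stated part of a secondary objective has no analysis in the SAP. The same added paragraph answers both.

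**Conclusion.** The concern holds in conditional form. The SAP describes no test for the parametric map, and the only rule it offers would mislead if applied per voxel: on average about 25–35 cm³ (upper tail of a two-sided test) or 50–70 cm³ (one-sided) of unaffected brain would appear increased. The volumes rest on an assumed brain of 1,000–1,400 cm³ and on a valid 0.05 test in each voxel. They are expectations, and single patients can fall well outside them when noise is shared across the brain.

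The reach is limited to one part of a secondary objective in a study the SAP calls exploratory. It would be tempting to conclude that the regional SUVR comparisons, or the aim of validating the quantification, are undermined as well. The documents do not support that: the regional results do not depend on a map threshold, and validation is listed as a separate purpose of the controls. The gap should be closed before any map of increased TSPO is reported.

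**What to change.** Add a short paragraph on the parametric map to the SAP:

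1. Exempt the map from the sentence that waives multiplicity correction. Leave the regional exploratory tests as they are.
2. State the unit of comparison (each patient against the controls, or group against group) and whether the test is one- or two-sided.
3. Define an increase by a brain-wide false-discovery-rate or cluster-extent threshold, with its level and any cluster-forming threshold given.
4. If single-patient maps are made, use the t limit with 14 degrees of freedom and the factor √(1 + 1/15) in place of a normal cut-off.
5. Compare each control with the other 14 (so 13 degrees of freedom and √(1 + 1/14)) and report the flagged volume as the empirical false-positive floor. This also picks up shared noise and non-normality, the main uncertainties above. It speaks most directly to single-subject maps.

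No new scans are needed. The cost is SAP wording and re-analysis of existing PET data; the documents show SUV maps but no thresholded statistical maps, so some of this may be first-time work. The downside is a smaller reported extent and, with only 15 controls, low sensitivity in corrected maps, above all for single patients. The SAP should say so.
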